***Intervention conditions:***

[figure not shown]
**YES+ workshop.** Your Enlightened Side, plus more (YES+) is an four-day, 15-hour eclectic life skills workshop with a strong emphasis on breathing techniques and social connectedness to enhance stress management, intervene in the potential negative behavioral cycles, and improve overall well-being. In addition to specific contemplative techniques such as yoga, mindfulness meditation, and compassion meditation that help cultivate inner peace, YES+ incorporates discussions and other activities to facilitate social connectedness, leadership, and community service.

During the workshop, participants will have ample time to learn and practice the Sudarshan Kriya Yoga (SKY) technique, as well as to ask questions. SKY has four sequential, form- and rhythm-specific breathing components interspersed with normal breathing while sitting in a relaxed position with eyes closed, followed by Yoga Nidra (tranquil state of rest) for 10-15 minutes in a supine position, yielding a total duration of approximately 30 minutes for the entire home practice. A longer version of SKY will be practiced as a group twice during the workshop. Following the workshop, participants will be instructed to practice SKY at home daily. A certified instructor with a minimum of 1,000 hours of SKY instruction training will lead each workshop.

**WOW! workshop.** A comparison workshop titled “Wisdom On Wellness” (WOW!) will be implemented to control for potential expectancy effects, time commitment, group-based interactions, and wisdom/knowledge of YES+ that is anticipated to have beneficial effects on stress management and well-being, allowing for more rigorous evaluation of the contemplative practices and other activities unique to the YES+ workshop. The material used to guide interactions in WOW! will be similar to the material of YES+ and will be taught by a trained instructor with supervision by the Principal Investigator and Study Coordinator. This workshop differs from YES+ due to the increased focus on cognitive approaches to conceptualizing and managing stress (e.g. thoughts about the past and future versus present moment), and absence of physical or somatic activities. Using a focus group format, whereby the instructor primarily facilitates discussion, a variety of topics will be covered such as the nature of stress for humans, response to stressful events, time management, study skills, alcohol and drug use, personal values, career exploration, sleep habits, and nutrition.

***Experimental manipulations:***

**Stress Induction.** The Maastricht Acute Stress Test (MAST), a previously described and increasingly used stress induction task, will be utilized. A research staff member in a white laboratory coat will explain that the session will be video-recorded to then be coded afterwards by trained raters, provide background information regarding performance norms, and express an expected ability of the participant to perform comparably. Next, the researcher will provide instructions for the task that will be guided by a Powerpoint presentation. The MAST consists of a 10 minute acute stress phase that combines elements of both the commonly used Cold Pressor Test and Trier Social Stress Test, adding an element of uncertainty by cycling between these two tests at slightly unpredictable time intervals (Figure 3). For the hand immersion trials (HIT), participants will insert their dominant hand and wrist in a bucket of ice water (approximately 2° C) for up to 90 seconds. Participants are instructed they may remove their hand at any time. Upon removal, participants will place their hand on a towel and immediately begin a serial subtraction task, for which participants will be instructed to count backwards by 13, 17, or 18 from a randomly selected number between 2013 and 2073, with interjections to start over from the beginning if any calculations are incorrect. Neutral or negative feedback will be provided throughout the task, including comments such as “That’s wrong. Start over” and “You’re going too slowly.”

**Figure 3.** Overview of Maastricht Acute Stress Test (MAST). Adapted from Smeets et al., *Psychoneuroendocrinology*, 2012.

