**8) Research procedures involved in the Human Research**

An overview of the study involvement is illustrated in Figure 1. Participation will include three laboratory visits at pre-workshop (T1), post-workshop (T2), and 1-2 month follow-up (T3) time points and four workshop sessions described below.

**Figure 1.** Overview of study timeline for each participant.

*Screening:* Interested participants will first be directed to an online pre-screening survey. The survey will begin with a prompt describing the study and requiring understanding via checkbox that the survey is for screening purposes. The survey will collect information such as name, e-mail address, date of birth, motivation for the study, student status, prior contemplative practice experience, ability to meet the time commitment, panic and bipolar symptoms, and potential affiliation with other

participants. If any of the exclusion criteria indicated above are met, the participant will be notified of ineligibility.

[figure not shown]
*Enrollment and randomization:* Eligible participants will be first grouped in clusters with any other participants with known affiliations stated in the online screener, in order to minimize possibility of learning about material of the other workshop, then assigned a workshop via random number generator.

*Laboratory Visits:* In-person laboratory visits will be conducted at the University of Arizona Respiratory Physiology Laboratory on the main UA campus. Workshops will be conducted in various buildings on the main UA campus depending on reservation availability.

Actigraphy, sleep diary, online questionnaires and practice logs measures will be completely remotely after the instruments are provided to participants during an in-laboratory visit.

In addition to actigraphy, sleep diary, online questionnaires, and home practice logs (for T2 and T3 time points) the following data will be collected during each laboratory visit: electrocardiography (ECG) with concurrent respiratory inductance plethysmography (RIP) and pulse oximetry recordings, as well as salivary cortisol at baseline, post-stress induction task, 30-min post-stress-induction-onset, and 45-min post. ECG, RIP belts, and pulse oximetry will be recorded continuously, in addition to the designated resting recording periods. An overview of the laboratory visit (identical across T1, T2 and T3) is provided in Figure 2.

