Effects of Two Psychosocial Wellness Workshops on Sleep, Stress Management and Wellbeing: Exploration of Psychophysiological Mechanisms

Brief title: Student Wellness Workshop study (SWW)

NTC number: not yet assigned

Date of document: 12/15/2017

Statistical analysis will be conducted in IBM SPSS 24.0 using Linear Mixed Models and selective post-hoc comparisons focusing on within-group change for YESplus and WOW at post and follow-up compared to pre-workshop. For each model, results will be reported for main effects of Visit (pre, post, follow-up) and Group (YESplus, WOW), as well as Visit x Group interaction. However, due to limited statistical power of this sample to detect interactions, analysis will focus on within-group change from pre- to post-workshop, as well as pre to follow-up, and corresponding within-group effect size. Thus, to balance type I and type II error with these within-group comparisons, a Bonferroni correction will be applied by multiplying uncorrected p values by 4 (the number of post-hoc comparisons per model), allowing alpha to remain at .05 for significance. Effect size estimates will be calculated with Cohen's d.

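### The stress task is repeated at all three visits in both arms, so a within-arm fall in its outcomes can reflect repetition; workshop claims for these outcomes should rest on Visit x Group

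*Protocol*

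**What the plan says.** Protocol Section 3, item 8, plans "three laboratory visits at pre-workshop (T1), post-workshop (T2), and 1-2 month follow-up (T3) time points". It adds: "An overview of the laboratory visit (identical across T1, T2 and T3) is provided in Figure 2". Each visit collects "salivary cortisol at baseline, post-stress induction task, 30-min post-stress-induction-onset, and 45-min post", with resting ECG recordings at the same points and 0-100 visual analogue ratings of discomfort/pain and distress throughout.

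Under Experimental manipulations, the MAST alternates ice-water immersion with serial subtraction, "adding an element of uncertainty by cycling between these two tests at slightly unpredictable time intervals". Participants are told that "the session will be video-recorded to then be coded afterwards by trained raters" and are given performance norms. "Neutral or negative feedback will be provided throughout the task". The one element stated to vary is the arithmetic: participants "count backwards by 13, 17, or 18 from a randomly selected number between 2013 and 2073". No rule is given for alternating these numbers across visits.

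The SAP fits linear mixed models and reports Visit, Group and Visit x Group. Citing limited power for interactions, it says that "analysis will focus on within-group change from pre- to post-workshop, as well as pre to follow-up", with within-group Cohen's d. It multiplies p values by 4, the number of post-hoc comparisons per model. Neither document mentions habituation or how a repetition effect would be separated from a workshop effect.

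**The concern.** Uncertainty and the threat of being evaluated are deliberate parts of this stressor, and both may weaken once a person has been through it. T1 is everyone's first exposure, T2 the second and T3 the third. Within one arm, the number of exposures and the time relative to the workshop are the same variable, so change from T1 contains both and the data of that arm alone cannot divide them.

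This matters because of where the SAP puts its weight. The protocol's Purpose names heart rate variability and salivary cortisol with a stress induction task among its aims. Under the SAP, a fall in either would be tested against zero within each arm and summarised as a within-group d. A reader would naturally take that as reduced stress reactivity due to the workshop. A result that is significant in one arm only would look like a workshop-specific benefit, although the arms had not been compared.

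**Working it through.** **Inputs from the documents.** N = 100 (Protocol, Study Population); two arms; two contrasts with T1 (T2 and T3); p values multiplied by 4 with alpha .05 (SAP).

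**Assumptions.** No allocation ratio is stated, so 50 per arm is assumed, with 40 per arm as a check. The documents give no repetition effect, so dz (mean change divided by the SD of change) is set at 0.2 to 0.5, equal in both arms, with no workshop effect. Clustering by workshop group or by affiliation is ignored, and a paired t-test stands in for the mixed-model contrast.

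**The plan's own figure.** 2 arms x 2 contrasts = 4 comparisons, so each is tested at .05/4 = .0125, and 4 x .0125 = .05. The factor is right. It controls the number of tests; it does not correct a null hypothesis that is false because of repetition.

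**Step 1: one arm, T1 to T2.** The rejection probability is P(|T| > t*), where T is noncentral t with n - 1 degrees of freedom and noncentrality dz x sqrt(n). For n = 50, t* = 2.593; for n = 40, t* = 2.619. For example, dz = 0.3 and n = 50 give noncentrality 0.3 x 7.071 = 2.121 and probability .329.

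**Step 2: two independent arms, 50 each.** At least one significant: 1 - (1 - p)^2. Exactly one significant: 2p(1 - p).

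| dz from repetition alone | Given arm, n = 50 | Given arm, n = 40 | At least one arm, n = 50 | Exactly one arm, n = 50 |
|---|---|---|---|---|
| 0 | .0125 | .0125 | .02 | .02 |
| 0.2 | .13 | .10 | .24 | .23 |
| 0.3 | .33 | .25 | .55 | .44 |
| 0.4 | .60 | .47 | .84 | .48 |
| 0.5 | .82 | .70 | .97 | .29 |

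**Step 3: the between-arm contrast.** Let the mean change in each arm be the repetition shift r plus that arm's workshop effect. The difference in change is (r + w1) - (r + w2) = w1 - w2, so r drops out. In 20,000 simulated trials per setting, with no workshop effect and shifts from 0 to 0.8 SD, a between-arm t-test on change at .05 rejected in about 5% throughout.

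**Step 4: what that contrast can detect.** The difference in change detectable with 80% power at two-sided .05 is (1.960 + 0.842) x sqrt(2/n) SD of change. This is 2.802 x 0.200 = 0.56 at 50 per arm and 2.802 x 0.224 = 0.63 at 40 per arm. Power for a difference of 0.3 SD at 50 per arm is about 32%.

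**The case against.** The strongest reply is that the design already deals with repetition. Both randomised arms do the same task on the same schedule, and the SAP reports Visit x Group for every model. That is correct, and it means the trial can support a comparison free of any shared repetition effect. What remains is the SAP's stated emphasis on within-group change, which has no such protection.

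A second reply is that the within-group emphasis affects every outcome and is not peculiar to the MAST. This is also fair. The MAST outcomes nevertheless have a specific rival explanation, because uncertainty is built into the stressor, and so they merit their own statement.

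Several stronger readings are tempting but unsupported:

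- A reader might infer that responses are bound to fall on repetition. The documents give no such figure; they support only that a fall can arise this way.
- A reader might infer that participants face an unchanged task each time. The start number is random and three subtrahends are listed. The word identical describes the visit overview, and the interval sequence is in a figure and a slide file that cannot be read here.
- A reader might infer that debriefing exposes the cover story before T3. A debrief document is listed, but its content and timing are not visible, so nothing can be concluded.
- A reader might propose counterbalanced task versions. These would balance version effects, but T2 would still be everyone's second exposure, so repetition would remain inseparable from Visit.

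Finally, the SAP names no outcomes. That its within-group focus covers the MAST measures follows from its applying to each model, together with the protocol's list of measures.

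**Conclusion.** The point holds as a limit on interpretation, and the remedy lies in the SAP. For cortisol and heart rate or its variability around the MAST, and for the visual analogue ratings, a within-arm fall from T1 cannot be separated from repeated exposure, and the Bonferroni factor does not change this. In the illustration, a repetition shift of 0.2 to 0.5 SD alone makes a given arm significant in 13% to 82% of trials at 50 per arm, or 10% to 70% at 40 per arm. These figures depend on the assumed shift, equal arms, independent participants and no workshop effect; they show how sensitive the test is and do not predict this trial's result.

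It would go too far to say that the trial cannot test a workshop effect on stress reactivity. The randomised Visit x Group contrast can do so, provided that the repetition effect itself does not differ by arm for reasons unrelated to the workshops. Its limitation is power, which the SAP concedes.

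**What to change.** Add a short statement to the SAP covering the MAST outcomes (cortisol and heart rate or its variability around the task, and the visual analogue ratings):

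1. Any claim of a workshop effect rests on the Visit x Group contrast, reported as the between-arm difference in change from T1 to T2 and from T1 to T3, each with a confidence interval.
2. Within-arm changes and their Cohen's d are descriptive, include the effect of repeating the task, and will not be reported as workshop effects.
3. Significance in one arm but not the other will not be read as a difference between workshops.

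This needs no new data, visits or staff and can be made even if the laboratory visits are complete, since the interaction is already in the planned model. The price is that conclusions on these outcomes will be more cautious: at 50 per arm, differences in change much below about 0.56 SD will often be missed, and the confidence interval will show that openly.

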**Measures:**

**Sleep diaries.** Participants will be instructed to fill out a sleep diary for one week at each of the three time points. The sleep diary includes entries for the time that participants go to bed, turn off the lights, awake in the morning, and arise from bed in the morning. Participants also record sleep onset latency, the number and duration of awakenings, and quality of sleep (1 = very restless to 5 = very sound). From these items, the following weekly average sleep summary parameters will be computed: total sleep time (TST), time in bed (TIB), wake time after sleep onset (WASO), number of awakenings, sleep-onset latency (SOL), sleep quality, time of going to bed in the evening, time the lights are turned out with the intention to sleep (lights-out time), wake time in the morning (awakening time), time of getting out of bed in the morning (arising time), and sleep efficiency (SE) which is TST divided by sleep period time; the time from lights out to lights on at arising.

**Actigraphy.** Concurrent with the sleep diaries, participants will be instructed to wear a wrist Actiwatch (Philips Respironics) from the time of getting into bed until the time of getting out of bed for one week. Participants will be instructed to press a button on the face of the Actiwatch that serves as an event marker in the downloaded data on two occasions during each sleep period: when participants intend to fall asleep and when they awaken for the final time at the end of their sleep period. These markers serve as measures of lights-off and lights on times, providing outside boundaries for subsequent calculation of sleep onset and offset. When this is not done, the estimated lights-off and lights-on times given by the participant in their sleep diaries will be used. Sleep onset will be defined as the beginning of the first 5 min of contiguous quiescence with less than 30 sec of any recorded activity counts that occur after lights-off time as used in. Once lights off, lights on, sleep onset, and sleep offset are established, these four values will be entered into a sleep-scoring algorithm to identify WASO, and to calculate the sleep indexes of SOL, TST, and SE. In addition to providing an objective measure of sleep variables, actigraphy has been particularly useful in documenting sleep-wake circadian patterns.

**Questionnaires.** Participants will be asked to complete a custom survey inquiring about information such as GPA and self-rated stress of specific situations, as well as the Morningness-Eveningness Questionnaire (MEQ) with an online format at T1. In addition, participants will be asked to complete a custom survey inquiring about information such as current stress-management techniques, the short-form Mood and Anxiety Symptom Questionnaire (MASQ), Perceived Stress Scale (PSS), Pittsburgh Sleep Quality Index (PSQI), Big Five personality inventory (Big-5), Rosenberg Self-Esteem Scale (RSES), Satisfaction With Life Scale (SWLS), and Social Connectedness (SC) measures online for all three time points. During each laboratory visit, participants will also be asked to complete the state-specific items of the State-Trait Anxiety Inventory (STAI).

**Electrocardiogram (ECG) measures.** Individual electrodes will be placed at collarbone and lower ribcage locations to collect ECG recordings. Participants will be instructed to sit quietly for 2 minutes for each of the four resting recordings (baseline, post-stress, 30-min-post, 45-min-post). ECG data will then be processed to determine measures including resting heart rate (HR), heart rate variability (HRV), and

respiratory sinus arrhythmia (RSA). Supplementary HR data will be collected via pulse oximetry, a device consisting of a soft clip placed around the participant's pointer finger. To control for respiration that may influence HR data, respiratory inductance plethysmography will be recorded concurrently via two adjustable belts placed around the participant's abdomen, one passing around the sternum and the other passing around the navel. As an additional covariate of Body Mass Index (BMI) for ECG analysis, height and weight will also be measured at each laboratory visit.

**Salivary cortisol.** In conjunction with the ECG recordings, saliva samples will be collected using Salivettes (Sarstedt, Nümbrecht, Germany). Participants will be instructed to avoid particularly stressful activities or events on the day of the laboratory visit prior to data collection in order to minimize potential effects on cortisol secretion and maximize data specific to the stress-induction task. In addition, participants will be asked to refrain from drinking, eating, and any dental hygiene for the 15 minutes prior to the arriving for the laboratory visit, which will also be confirmed verbally prior to the first sample collection. Following data collection, samples will be stored in a freezer at -70 °C on the University of Arizona campus. Samples will then be de-identified and shipped to an independent site for high sensitivity enzyme-linked immunosorbent assay (ELISA) preparation.

**Visual Analog Scales (VAS).** To assess momentary stress-related ratings, Visual Analog Scale (VAS) measures will be collected throughout each laboratory visit. VAS measures will include items such as "discomfort/pain" and "distress" with a 0-100 scale corresponding to low and high values for each item. One of the two researchers conducting the experimental session will present a whiteboard with the scales to the participant at each measurement point and will ask the participant to simply wipe a single point along the temporarily drawn horizontal line for each scale. The score for analysis will be the nearest 5-pt value on a scale of 0 to 100 (e.g. 35) of the wiped mark, judged by the researcher. The researcher will transfer the two rating scores to a recording sheet, erase both temporary lines, and redraw them using a straight-edged guide to be ready for the next measurement. The whiteboard with each of the participant's ratings (wiped marks) will be visible to the videorecorder in case time between measurements (e.g. during the MAST) does not allow for transfer of the information to the recording sheet while the experiment is in progress.

**Workshop expectancy evaluations.** To assess potential expectancy effects, both participants and workshop instructors will be asked to complete a short questionnaire at the end of the first and final days of the workshop. Questions will inquire about information such as confidence in anticipated benefit, willingness, credibility, and likelihood to recommend to others. These questionnaires follow a format of previously used and validated expectancy scales.

**Home practice logs.** Participants will be asked to track daily practice of any techniques provided from the workshops. In order to maintain consistency across participants and workshops, the same log will be provided to everyone. An example entry for the yogic breathing-based workshop (YES+) may be the use of a specific breathing technique prior to an exam. An example entry for the psychoeducation workshop (WOW!) may be the use of a cognitive strategy such as recognizing that an exam grade is only a portion of a final semester grade.

## 9) Cost to subjects

*There is no monetary cost to the subject, although participation in the study involves time to complete the online screening, measures associated with the three laboratory visits, and workshop.*

